## **9. Ethics**

The study proposal and patient consent form has been approved by the Research Ethics Boards at the Canadian College of Naturopathic Medicine, The Ottawa Hospital, participating multicenter sites, and by The Natural Health Products Directorate. Ethics Committees and the Data and Safety Management Board are provided with annual progress reports.

## **10. Study Timetable**

Recruitment for this trial will take a total of eight years to complete, with an expected end date of January 2015. Following the closing of recruitment primary outcomes will be assessed. The study will be closed and all data finalized, two years following enrollment of the last participant. Dissemination will take place through publication in a high impact journal, through conference presentations at national and international conferences, and to lung cancer patients through outreach to patient advocate groups and societies.

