## **6.3 Recruitment and screening**

Patients will be identified and selected prospectively from investigators' patient records. Entry into the trial may occur pre- or post-operatively, up to the point at which the trial intervention begins on the day of discharge from hospital up to 60 days after surgery. Even though there is a recruitment window of 60 days, it is important to enroll patients as soon as possible after surgery. Recruitment and patient accrual will occur during the first five years of the trial. To facilitate the enrollment REB approved informative brochures about the study may be placed in appropriate locations (i.e., exam rooms and waiting rooms). Recruitment for the 80 patients in the sub-study will be done post-operatively, as they will need to have a baseline blood draw at their first post-operative appointment.

The trial began enrollment in Oct 2007, and we have currently have eight sites including the Ottawa Hospital actively recruiting patients. Dissemination of the trial results will take place through publication in a high impact journal, through conference presentations, and to lung cancer patients via outreach to patient advocate groups and societies.

In all presentations of the phase III trial, the funding contributions of the Lotte and John Hecht Memorial Foundation and the Gateway for Cancer Research will be acknowledged. In all presentations of the phase II substudy, Gateway's sole contribution and support will be acknowledged.

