#### **6.4 Interventions**

Patients who appear to meet eligibility criteria will be approached and asked to consent to the trial by the research coordinator. After eligibility criteria have been confirmed by the investigator or medically qualified delegate patients will be randomized using a centralized system at The Ottawa Hospital to either active melatonin group or placebo. Randomization will be stratified according to cancer staging (I/II vs. III/IV). Allocation bias will be prevented by using a randomization table with variable blocks of 4 and 6. Only the Pharmacy Research Technician at the Ottawa Hospital can see the randomization table and treatment assignments.

Patients, physicians, and the research coordinator will be kept strictly blinded as to individual group allocation and treatment. The intervention, active or placebo, will be given to participants in opaque bottles with the patient study code clearly written on the corresponding container. The clinical trial pharmacist at the coordinating site will be responsible for the coding and container labeling of all containers. Instructions for taking the intervention will be identical for both control and melatonin groups. The research coordinator will be responsible for the dispensing of the pills (both active and placebo).

Melatonin or placebo will be provided to patients either on the day of discharge or up to 60 days post-operative from the hospital. In the phase II substudy, participants will only be given the intervention four weeks following surgery. This wait period is to reduce the confounding effect of the surgery on the surrogate measures we are testing. Patients will be responsible for taking their doses and will be required to report any missed doses to the research coordinator. To ensure optimal compliance, the research coordinator will telephone each patient once a week for two weeks at the beginning of the trial. Telephone calls will then be made as needed until the completion of one year while the patient is on the study drug.

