## **6.5 Outcome Measures**

The primary outcome is a composite outcome including either cancer recurrence and/or mortality within two years following the commencement of the intervention. Recurrence will be determined by clinical examination by the patient's thoracic surgeon in addition to radiological evidence of loco-regional or systemic recurrence of lung cancer. While contrast enhanced chest CT scan at one and two years post resection is the preferred radiological assessment, the standard of care radiological assessments for each site is acceptable. For study purposes, only chest CT is requested at 1 and 2 years, but results of head and abdominal CTs will be recorded if applicable. As per standard of care, lateral and P/A chest radiographs will be assessed at 3 weeks and at 3, 6, 9, 12, 18 and 24 months following hospital discharge.

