## NSCLC Adjuvant melatonin RCT

months, 9 months, 1 year, 18 months and 2 years. Information regarding the results from chest x-rays or CT scans, chemotherapy and/or radiotherapy treatment, recurrence and past medical history/concomitant medications will be captured from the patient's chart. All other information will be captured by the research coordinator through telephone conversations and follow up visits with the patients.

The research coordinator will make a follow up phone call once per week for the first two weeks and then as needed for the one year while the patient is on the study drug. During telephone conversations, the research coordinator will assess study compliance and any adverse or serious adverse events. Information regarding these phone calls will be captured in the patient's study records.

At follow up appointments, the research coordinator will provide the patient with study drug refills (up to the 1-year mark), provide quality of life questionnaires, monitor any adverse or serious adverse events and monitor compliance. Compliance will be monitored during a brief interview, and by checking for left over pills. Patient self-report is an acceptable measure of compliance if counting pills is not feasible. Patients will be asked at each follow-up phone call and visit if they have missed any capsules. Patient reports of start and end dates of the capsules will also be used to determine compliance.

The study will be extended to include follow up periods past the initial follow up period of two years. Specifically, patient follow up times will be extended to include follow ups with all patients enrolled on study beginning in 2007. Patients' records will be tracked to determine whether they experienced a recurrence or death. Participants will be followed until they either reach the five year maximum or until 2 years after the last participant was enrolled in the study. As such, each patient will have a varying follow up period (with a range of 2-5 years).

Extension of follow ups past the two year time point will be conducted as follows:

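### The data close is counted from the last enrolment and the two-year primary window from the first capsule, so the close can fall before the last-enrolled patients complete that window

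*Combined protocol and SAP*

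**What the plan says.** The protocol sets the end of data collection on one clock and the primary outcome on another.

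- **Close.** Section 10: "The study will be closed and all data finalized, two years following enrollment of the last participant". Section 6.6 agrees: each patient is followed to a five-year maximum or "until 2 years after the last participant was enrolled in the study". It gives the resulting follow-up per patient as two to five years.
- **Primary outcome.** Section 6.5 counts recurrence or death "within two years following the commencement of the intervention". The preferred CT is timed from resection (one and two years), and the last radiograph is at 24 months from discharge.
- **Enrolment and first capsule.** Section 6.3: "Entry into the trial may occur pre- or post-operatively, up to the point at which the trial intervention begins". The intervention itself "begins on the day of discharge from hospital up to 60 days after surgery". Section 6.4 repeats the 60-day limit. In the sub-study, capsules start four weeks after surgery.
- **Analysis.** Section 8 specifies an unadjusted chi-square test on the two-year event proportions. It has no censoring and no rule for a patient whose window is incomplete at the close.
- **Timing of assessment.** Section 10 also says: "Following the closing of recruitment primary outcomes will be assessed".

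The enrolment date is not defined as consent or as randomization. The interval from a pre-operative enrolment to surgery is not given.

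**The concern.** Enrolment cannot follow the first capsule, but it may precede it by weeks. Two years from the last enrolment is therefore the latest close that could still be adequate, and it is adequate only if the last patients start capsules on the day they enrol. Otherwise the end of their window lies beyond the date on which all data are final.

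Three things could be lost: events in the last weeks of those windows; for patients enrolled before surgery, the two-year CT, at which a symptomless recurrence may first be seen; and time for the search in section 6.6, which runs from medical records through the cancer registry, family doctor, other facilities, letter and telephone to next of kin. Because the analysis is a fixed two-year proportion, a patient whose event falls in the lost weeks, or would be detected only then, is counted as a non-event or becomes missing, and no rule says which.

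**Working it through.** **1. The plan's own figure.** Section 6.6 gives a minimum follow-up of two years. On the enrolment clock this reproduces: close = last enrolment + 730 days, so the minimum is 730 days. On the primary-outcome clock the minimum is 730 − g, where g is the gap in days from enrolment to first capsule:

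- g = 0: 730 days
- g = 28: 702 days
- g = 60: 670 days
- g = 120: 610 days

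The two-year minimum holds on the outcome clock only at g = 0.

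**2. Inputs.** N = 640, 320 per arm (section 7.0). Accrual is taken as even over 96 months (section 10, eight years) or 87 months (October 2007 in section 6.3 to January 2015 in section 10). The gaps are assumptions: 28 days matches the sub-study's four weeks from surgery, 60 days is the limit for someone enrolled at surgery, and 120 days adds an assumed 60-day pre-operative wait. Event rates of 5% and 20% are those of section 7.0.

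**3. Patients with an incomplete window.** A patient is cut off if enrolled within g days of the last enrolment, so the number is (640 / accrual days) × g. Over 96 months the rate is 640 / 2922 = 0.219 per day; over 87 months it is 640 / 2648 = 0.242 per day.

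| Accrual | g = 28 | g = 60 | g = 120 |
|---|---|---|---|
| 96 months | 6.1 (1.0%) | 13.1 (2.1%) | 26.3 (4.1%) |
| 87 months | 6.8 (1.1%) | 14.5 (2.3%) | 29.0 (4.5%) |

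The days lost are spread evenly over 0 to g, so the mean loss is g/2, for example 30 of 730 days at g = 60.

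**4. Expected events lost, constant hazard.** With two-year rate p, the daily hazard is h = −ln(1 − p)/730, and the loss is approximately (patients cut) × (1 − p) × h × g/2. At g = 60, 96 months and p = 0.20, h = 0.000306 and the loss is 13.1 × 0.80 × 0.000306 × 30 ≈ 0.10. The exact results, for p = 5% and then 20%, are:

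| Accrual | g = 28 | g = 60 | g = 120 |
|---|---|---|---|
| 96 months | 0.006; 0.021 | 0.026; 0.097 | 0.106; 0.390 |
| 87 months | 0.006; 0.023 | 0.029; 0.107 | 0.116; 0.431 |

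If late accrual ran at twice the 96-month average and g = 120, the loss would be 0.21 and 0.78 events. A 40% event rate, taken only as a sensitivity value, would bring that to 1.36.

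**5. The final CT.** For a patient enrolled w days before surgery, the CT at two years after resection is due w days after that patient's second enrolment anniversary. For a patient enrolled after surgery it is due before that anniversary, so the close does not remove it. The number affected depends on w. At w = 60 and the 96-month rate it is about 13. If, as an upper guide, half of a 20% event rate falls in year 2 and is found only at that scan, the loss is 13 × 0.20 × 0.5 = 1.3 events.

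**6. Power.** For 5% versus 12% with 320 per arm and two-sided alpha 0.05 (assumed, since none is stated), power is 88.97% with full windows, 88.94% at g = 60 over 96 months, and 88.76% at g = 120 with doubled accrual.

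**The case against.** The strongest reply is that this is a mismatch of wording with almost no numerical effect. Section 6.3 allows the gap to be zero. The two-year minimum in section 6.6 shows the intent to observe everyone for two years. Most affected patients would still be classified correctly, and because the gap arises under blinding the loss should be similar in the two arms. All of that stands, and it limits the point to a correction of the closing rule. A zero gap is permitted but not assured: section 4 describes participants as scheduled for resection, and section 6.6 provides a form for patients enrolled who never started the intervention. Even at zero gap, the last window ends on the day the data are final, with no time for the search.

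It can also be said that counting the outcome from enrolment would remove the conflict. It largely would, since a close two years after the last enrolment would then complete every window. What would remain is the CT of patients enrolled before surgery, which would still fall late, and the retrieval allowance.

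Two stronger readings are tempting. A reader might infer from "Following the closing of recruitment primary outcomes will be assessed" that the primary outcome is to be analysed when recruitment stops, as an early look while the most recent patients are still short of two years. The documents do not support this. The sentence sets no analysis date, the next one finalises the data two years later, and sections 6.5 and 6.6 schedule two-year assessments. Section 6.8 mentions interim analyses for the monitoring board but ties none to the end of recruitment. A reader might also infer that all late-enrolled patients lose the two-year scan. That applies only to those enrolled before surgery.

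**Conclusion.** The point holds as a conflict between a stated rule and the endpoint definition. The close in sections 6.6 and 10 can fall before the last-enrolled patients complete the window in section 6.5, and no rule covers those whose window is incomplete.

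Its size is small: about 6 to 29 patients (1% to 4.5%), usually less than one expected event, about 1.3 if recurrences found only at the final scan are missed, and a negligible change in power. These figures rest on even accrual, one common gap for all patients, a constant hazard and assumed gaps of 28 to 120 days; a faster finish to recruitment would raise them. The documents do not establish that any patient will in fact be cut off, because the enrolment date is undefined and the gap may be zero.

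The reason to act is not power. A trial with a fixed two-year primary outcome should have a closing rule that guarantees two years of data on the clock of that outcome.

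**What to change.** - In sections 6.6 and 10, define the close as the date on which the last participant has completed two years from the primary-outcome time zero and has passed the two-year CT date, plus a stated allowance for scan results and record retrieval.
- In section 10, reword the sentence on assessing primary outcomes to say that the primary analysis is done once, after that close.
- Define the enrolment date (consent or randomization), so that the two-year minimum in section 6.6 can be checked against the outcome window.

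The cost is a few sentences and a close that moves by a few months. No treatment or visit changes.

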### **Clinical Site/Coordinating Center:**

In conjunction with a highly effective inter-disciplinary team of respirologists, radiologists and oncologists, the five thoracic surgeons who comprise the Division of Thoracic Surgery at the University of Ottawa at The Ottawa Hospital currently treat more lung cancer patients than in any other center in Ontario, and perform the largest number of pulmonary resections than any other group. Working in a group practice, the Division is known for its cohesive and comprehensive care of lung cancer. The Division is a leading center of Thoracic Surgery in Canada, with numerous research and administrative contributions recognized nationally and internationally.

## **12. Feasibility**

The combination of expertise in lung cancer treatment, natural health products, cancer research, and trial methodology in an ideal clinical setting puts our team of investigators in the position to fully address the objectives laid out. The assembled team of investigators includes all the people needed to successfully complete the trial including a naturopathic doctor, four thoracic surgeons, two epidemiologists, a medical oncologist, and a radiation oncologist. With the support of the Lotte and John Hecht Foundation, this seminal partnership between The Canadian College of Naturopathic Medicine and The Ottawa Hospital have the combined resources to effectively execute and complete this very important clinical trial.

The specific benefits of partnering with The Ottawa Hospital are considerable. Primarily, the Department of Thoracic Surgeons sees one of the highest volumes of lung cancer patients eligible for surgical resection in all of Canada. Affiliation with this group allows the accrual of enough patients in a single center, thereby substantially reducing the associated costs and complexity of the trial. With regards to this, The Ottawa Hospital Research Institute (OHRI) has recognized that this trial will not be benefiting from the usual support obtained from the pharmaceutical industry. Based on this and the novelty of the trial, the OHRI has graciously agreed not to add its usual 25% overhead costs. A further cost reduction has been achieved by securing the commitment from SISU Inc. (the supplier that provided the melatonin/placebo capsules for the first phase of the trial) to provide both the melatonin and placebo free of cost. This contribution has a market value of approximately \$ 50,000. It is essential to note that this donation is made with no company input or direction on trial design or with any limitations or requirements for post-trial publication and dissemination.

## **13. Dissemination/Knowledge Transfer**

Given the important and innovative aspects of this study, widespread dissemination of the trial results will be performed. This will include scientific presentation to both alternative and traditional medical societies within Canada and internationally. Presentations will be accompanied by published abstracts. However, the principal mechanism for knowledge transfer will be publication. We will target the most reputable clinical journals for publication due to the potential impact of this investigation (e.g. New England Journal of Medicine, Lancet, or British Medical Journal). Lastly, presentation of the results will be performed locally in Ottawa and Toronto through Grand Rounds and other educational round opportunities. We will additionally translate our findings for cancer patients and lay persons through presentations primarily at lung cancer support societies.

## **14. Relevance and Impact**

Lung cancer kills far more men and women than any other cancer. Despite advances in surgical therapy and decades of research regarding chemotherapy, recurrence rates leading to mortality remain unacceptably high. The potential for relatively benign natural health products to improve outcomes remains an attractive therapeutic modality too often ignored by the medical profession. Melatonin has strong but not definitive evidence supporting its use as an anti-neoplastic agent. A properly performed large randomized clinical trial is essential to evaluate the clinical value of this therapy. If proven effective, this trial will be the most effective way to allow lung cancer

## NSCLC Adjuvant melatonin RCT

patients to benefit from melatonin, as well as demonstrating the potential value of natural health products within mainstream health care in general. Conversely, if proven ineffective, the large number of patients currently taking melatonin with inadequate evidence to support its use will have good evidence to discontinue its use.

Although results from small trials testing the benefits of adjuvant melatonin in NSCLC are encouraging, confirmation from an independently based trial is necessary. The trial proposed is properly powered and rigorously designed so as to answer the question of the effectiveness of melatonin in the prevention of lung cancer recurrence and mortality at 2-years. The fact that lung cancer is such a deadly disease with truly inadequate conventional therapies underscores the importance of testing novel treatment regimes. Melatonin is an example of a natural health product with extensive and mostly positive research on its potential anticancer effects. What is interesting about melatonin is that it has no traction as a treatment protocol in conventional settings as it is not a patented pharmaceutical drug. By conducting a well-powered, rigorous trial, we aim to address the question of the effectiveness of melatonin head on and provide conclusive answers for this potentially lifesaving adjuvant therapy.

In addition to testing the therapy itself, the execution of a clinical trial like this in a well-known research hospital will have the important net effect of introducing a therapeutic agent that has not sprung from the pharmaceutical industry. Instead, a conventional medical institution will be collaborating with CCNM, an institution dedicated to the training and research of complementary and alternative medicines, towards the research of a natural health product.

The public is adopting natural medicines as a regular part of their personal health choices. According to Health Canada's website, a recent survey showed that 71% of Canadians regularly take vitamins and minerals, herbal products, homeopathic medicines and the like - products used in complementary and alternative medicine that have come to be known as natural health products (NHPs). With such a large percentage of the population interested in using NHPs to improve their health, there has been a serious deficiency in the number of scientifically controlled studies to prove the benefits and harms of these products. Since NHPs are often not patentable, there is little funding from traditional pharmaceutical or other for-profit agencies to support these scientific studies. With only anecdotal evidence to inform decision making, we know that many patients are being harmed by the improper use of NHPs and many more are not receiving the benefits.

This study is unique. By working in partnership with an academic health science centre, with well-established and qualified clinical researchers, by applying the same rigid standards to this research as to any other clinical pharmaceutical research, the investigators are taking a step forward in forging a new method of conducting critically needed research into NHPs. This kind of research is critical because it meets the needs of the medical community for rigorous, scientific methodology, with consideration given to the differences in studying NHPs. The impact of these partnerships in future endeavours cannot be understated. Many organizations and investigators will be monitoring this study to learn and develop their own research and partnerships. The significance of this study is not limited to its importance for the patient with lung cancer, but it will have a wide impact on the credibility of scientifically funding and testing NHPs throughout Canada.

